4 PATIENT SELECTION

4.1 Inclusion Criteria

A patient must meet all of the following inclusion criteria to be eligible to participate in the study:

- 4.1.1 Pathologically confirmed high-grade glioma (WHO grade 3 or 4), with documented CT or MRI progression or recurrence. Biopsy is also an acceptable method of confirming progression. If initial tumor was grade 2 glioma, histological confirmation of high-grade recurrence is required.
- After first interim analysis, if the study proceeds to enrollment of selected patients (only those who have PDGFR α -positive tumors), patients will be pre-registered for PDGFR α analysis and registered to the combination treatment schema only if PDGFR α -positive and all other enrollment criteria are met.
- 4.1.2 Measurable or evaluable disease by RANO (MRI) or Macdonald (CT) criteria (see Section [10.2](#)).
- 4.1.3 Fixed or decreasing dose of corticosteroids (or no corticosteroids) for at least 1 week prior to cycle 1 day 1.
- 4.1.4 Age \geq 18 years.
- 4.1.5 At least 12 weeks since the completion of radiation therapy to a total of \geq 50 Gy.

4.1.6 ECOG performance status of 0, 1, or 2 ([Appendix 1](#)).

4.1.7 Clinical laboratory parameters:

- WBC $\geq 3,000/\text{mm}^3$
- ANC $\geq 1,500/\text{mm}^3$
- Platelets $\geq 100,000/\text{mm}^3$
- Hgb ≥ 8.5 g/dL
- AST, ALT ≤ 3 x upper limit of normal (ULN) for the laboratory
- Total bilirubin ≤ 1.5 x ULN for the laboratory (total bilirubin criteria may be waived if a patient has documented Gilbert's disease)
- Creatinine clearance (CrCL) ≥ 30 mL/min as calculated by the standard Cockcroft-Gault equation ([Appendix 2](#))

4.1.8 Women of childbearing potential must have a negative serum pregnancy test performed within 7 days prior to the start of treatment.

4.1.9 Women of childbearing potential and men must agree to use a medically accepted form of birth control for the duration of study participation and for 2 months following completion of study treatment.

4.1.10 Ability to understand and the willingness to sign a written informed consent document.

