6 TREATMENT PLAN

6.1 Baseline Tests and Procedures

Refer to Section [12](#), Study Calendar, for the screening tests and procedures that are required prior to treatment and/or registration, and for the timing of these events relative to the start of combination treatment.

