6.2 Schedule

The treatment schedule is combined sorafenib, valproic acid, and sildenafil, administered orally, twice daily continuously. A cycle consists of 4 weeks. The first cycle begins once therapy begins with all 3 agents—after, if necessary, titration of valproic acid dosage, described in Section [6.2.7](#). Titration of valproic acid may occur as a matter of clinical preference, prior to study enrollment.

Study drug therapy is taken on an empty stomach, that is, at least 1 hour before or 2 hours after eating, due to absorption characteristics of sorafenib.

The first 6 patients evaluable for qualifying toxicity assessment will be treated as a safety lead-in; enrollment will be gated (the first 3 evaluable patients must complete 4 weeks of the combination therapy before the next 3 patients start combination treatment on protocol) and patients will undergo weekly evaluations for qualifying toxicities (Section [6.4.2](#)) during the first 4 weeks of combination therapy.

- 6.2.1 Initiation of sorafenib and sildenafil will not take place until valproic acid levels are \geq LLN for the laboratory, which generally takes 5-7 days after initiation.
- 6.2.2 Valproic acid will be administered orally, generally twice daily. The tablets or capsules should be swallowed without chewing to avoid local irritation of the mouth and throat. Patients who experience gastrointestinal irritation may benefit from administration of the drug with food or by slowly building up the dose from an initial low level.
- 6.2.3 If a patient is already on valproic acid and blood levels are \geq LLN for the laboratory, no further titration is necessary.
- 6.2.4 If a patient presents for evaluation for this study and are at risk for seizures, the patient may be started on valproic acid.
- 6.2.5 If a patient is already on non-valproic acid antiepileptic therapy, they may be transitioned to valproic acid, as a matter of clinical preference, prior to enrollment to obtain levels \geq LLN for the laboratory prior to discontinuing the original antiepileptic therapy.
- 6.2.6 Patients with disease recurrence require routine maintenance on antiepileptic therapy. If a patient presents for study evaluation before initiation of antiepileptic

medication, patient may start valproic acid titration to \geq LLN for the laboratory as a matter of clinical care.

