12 STUDY CALENDAR

Table 15. Study Calendar

Event	Baseline ^A	On Treatment ^B									Follow Up ^C	
		Cycle 1				Cycle 2				Cycle 3+	Initial 30-Day Period	Extended Period
		D1	D8	D15	D22	D1	D8	D15	D22	D1		
Informed Consent	X ^D											
Demographics, Height	X ^D											
History and Physical Exam including Performance Status, Dermatologic and Neurologic Assessments	X	X ^E	X ^F	X	X ^F	X		X		X		
Vital Signs, Weight	X	X	X ^F	X	X ^F	X		X		X		
Baseline Symptoms	X											
Adverse Event Assessment		X	X ^F	X	X ^F	X		X		X	X ^C	
Concurrent Medications, Including Steroid Dosing Review	X	X	X ^F	X	X ^F	X		X		X		
Study Medication Diary Review and Pill Count		X	X ^F	X	X ^F	X		X		X		
Pregnancy Test, Counseling	X ^G											
ECG	X		X ^H							X ^H		
Tumor Imaging	X ^I	X ^J										
Survival, Alternative Therapies										X ^C	X ^K	
Archived Tumor Tissue	X ^L											
CBC with Differential, Platelets	X	X ^B	X ^F	X	X ^F	X		X		X		
Basic Metabolic Panel, ^{M,N} Hepatic Panel, ^O Magnesium, ^N Phosphorus ^N	X	X ^B	X ^F	X	X ^F	X		X		X		
PT, INR ^P	X	X										
Serum Valproic Acid Level ^Q	X	X										
Serum Ammonia	X											
Valproic Acid	Initiate, titrate, and/or maintain level ≥ LLN for the laboratory and dose per Sections 6 and 9 .											
Sorafenib	Initiate on C1D1, provided valproic acid level is ≥ LLN for the laboratory; continue dosing per Sections 6 and 9 .											
Sildenafil												

- A. Within 2 weeks prior to enrollment unless otherwise noted.
- B. C1D1 labs do not need to be repeated on C1D1 if done within 7 days prior to initiation of study treatment. Other C1D1 assessments may be performed within 3 days prior to day 1 dosing. In cycle 1, weekly assessments must be done within +/- 1 day of required time point. In cycle 3 and subsequent cycles, assessments must be done within +/- 3 days of scheduled time point; greater variations in timing may be permitted after cycle 2, with prior principal investigator/designee notification. For patients who are still on study for longer than 36 months, assessments may be done every other cycle (approximately every 8 weeks).
- C. See Section [7.8](#): The 30-day post-treatment follow-up period is meant to capture resolution or stabilization of ongoing treatment-related AEs or evolution of new treatment-related AEs.
- D. Within 4 weeks prior to initiation of study treatment.

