- E. If baseline history and physical exam is performed on a day other than C1D1, a brief visit to determine neurologic stability on current dose of steroids is also required on day 1 or day before.
- F. Only patients in the safety lead-in cohort.
- G. For women capable of pregnancy: pregnancy test at baseline; subsequently, review pregnancy risks and offer pregnancy test
- H. First “on-treatment” ECG is done approximately C1D8-C1D15 to evaluate acute changes relative to the study drug combination; the second is done approximately C3D1 to evaluate changes after a more chronic dosing of study drug combination.
- I. MRI or contrast-enhanced CT within 3 weeks prior to enrollment. An MRI is the preferred modality in all patients without a contraindication to MRI. Baseline and follow-up scans must be performed using the same modality.
- J. Imaging to be done to assess response every 2 months from initiation of treatment until off-study due to patient withdrawal, progression, or death. If MRI or contrast-enhanced CT shows response then repeat after 1 month to confirm response and then follow every 2 months from time of confirmatory MRI or CT. Patients with symptoms suggestive of progression may have imaging done between regularly scheduled scans, any time there is clinical concern for progressive disease. See also Section [10.4](#).
- K. See Section [7.8](#): After stopping study treatment, capture initiation of new therapy, first new progression date, and/or survival status since last observation approximately every 2 months during extended follow-up.
- L. Obtain and analyze archived tumor tissue per Section [11](#). During enrollment of the initial PDGFR α -unselected subgroup (prior to first interim analysis), archived tumor tissue must be obtained and analyzed, but analysis does not need to be performed prior to enrollment. After the first interim analysis, if the study proceeds to include only PDGFR α -positive patients, archived specimen analysis for PDGFR α will be required, and results must be known, prior to enrollment.
- M. Sodium, potassium, carbonate, chloride, glucose, calcium, BUN, creatinine.
- N. Additional assessments may be done at investigator discretion in patients with congestive heart failure, bradyarrhythmias, those on drugs known to prolong the QT interval, including Class Ia and III antiarrhythmics, and electrolyte abnormalities.
- O. ALT, AST, ALP, total bilirubin, direct bilirubin, albumin, total protein.

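### The Study Calendar allows a pregnancy test up to 2 weeks before enrollment, while Section 4.1.8 requires one within 7 days before treatment starts

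*Combined protocol and SAP*

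**What the plan says.** Section 4.1.8 sets the eligibility rule: "Women of childbearing potential must have a negative serum pregnancy test performed within 7 days prior to the start of treatment".

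Section 6.1 refers the site to Section 12 for the required screening tests "and for the timing of these events relative to the start of combination treatment". In Table 15 the pregnancy test is marked only in the Baseline column. Footnote A gives the window for that column: "Within 2 weeks prior to enrollment unless otherwise noted". The row's own footnote, G, reads: "For women capable of pregnancy: pregnancy test at baseline; subsequently, review pregnancy risks and offer pregnancy test". It gives no window, does not refer to 4.1.8 and does not specify serum.

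Enrollment and the first combination dose need not coincide. Section 6.2 says: "The first cycle begins once therapy begins with all 3 agents", after any valproic acid titration that is needed. Under Section 6.2.1, "Initiation of sorafenib and sildenafil will not take place until valproic acid levels are" at or above the laboratory's lower limit of normal, "which generally takes 5-7 days after initiation". Section 4.2.4 does not require that level at enrollment. Section 6.2 says that titration may be done before enrollment but does not require it.

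**The concern.** The two rules differ in length (14 days against 7), in anchor (enrollment against start of treatment) and in whether the sample type is stated. A site that takes its timing from the calendar, as Section 6.1 directs, can obtain a test that fails an inclusion criterion.

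The test is both an eligibility condition and a safety check before three study drugs are given together. A woman could receive the first combination dose on a test older than the protocol accepts. Sites working from different sections would also record different eligibility deviations for the same conduct.

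**Working it through.** This is date arithmetic; no power or error-rate formula is involved.

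Inputs:
- Eligibility limit: 7 days before start of treatment (4.1.8).
- Calendar window: 14 days before enrollment (Table 15, footnote A).
- Titration: generally 5 to 7 days from the first valproic acid dose (6.2.1).
- Consent: within 4 weeks, that is 28 days, before study treatment begins (footnote D), and signed before any study-specific procedure (15.3).

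**Oldest calendar-compliant test.** Let g be the number of days from enrollment to cycle 1 day 1 (C1D1). The maximum age at C1D1 is 14 + g, and the excess over 4.1.8 is 14 + g − 7.

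| g (days) | Situation | Maximum age | Excess over 7 days |
|---|---|---|---|
| 0 | treatment on the day of enrollment | 14 + 0 = 14 | 7 |
| 5 | 5-day titration starting at enrollment | 14 + 5 = 19 | 12 |
| 7 | 7-day titration starting at enrollment | 14 + 7 = 21 | 14 |
| 14 | limit implied by the consent window | 14 + 14 = 28 | 21 |

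The calendar window does not reproduce the 7-day limit at any g.

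**When both rules can be met.** For a test t days before enrollment, both hold when t is between 0 and 14 and t + g is at most 7.

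| g (days) | Values of t that meet both rules |
|---|---|
| 0 | 0 to 7 |
| 3 | 0 to 4 |
| 5 | 0 to 2 |
| 7 | 0 only (day of enrollment) |
| 8 or more | none |

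At 8 days or more only a test after enrollment can meet 4.1.8 for the first combination dose, and Table 15 schedules none. Footnote G only has later tests offered. The 7-day allowance in footnote B concerns labs due on C1D1, and the pregnancy row has no C1D1 mark.

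**Does the exception clause in footnote A cover this?** Other rows that depart from the 2-week default say so in their own footnotes: D gives 4 weeks before treatment, and I gives 3 weeks before enrollment for imaging. G does not.

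**The case against.** The strongest reply is that the stricter rule governs. Section 4.1 requires every inclusion criterion to be met, Section 5.1 requires a completed eligibility checklist for registration, and footnote A is a default that gives way to exceptions. On that reading 4.1.8 is the exception and supplies the word serum, so a site that reads both sections tests late and complies. Contraception is also required separately (4.1.9).

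Much of this stands. When treatment starts within 7 days of enrollment the rules are compatible, and missing 4.1.8 would mean overlooking an explicit criterion. The silence of footnote G on serum is an omission rather than a contradiction. The reply does not cover the longer gap, where compliance needs a test that the calendar does not schedule. It also leaves the calendar, the place to which sites are sent for timing, without the operative window.

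It is also fair to say that 19 to 21 days is a permitted worst case. It needs a test on the earliest allowed day and valproic acid started at enrollment, although titration may come first and a patient already at the required level needs none (6.2.3).

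On the anchor, Section 4.2.4 places titration before study therapy, and Section 6.2 starts cycle 1 with all three agents. Both favor C1D1 as the start of treatment. Section 10.1, however, counts toxicity from the first dose of any of the three drugs, so the term is not settled.

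Section 9, the pharmaceutical information, is blacked out, and any pregnancy instruction there cannot be seen.

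**Conclusion.** The inconsistency is real and should be corrected. Its size without any assumption about titration is 14 days against 7. It reaches 19 to 21 days if titration follows enrollment, and about 28 days at most for a study-specific test. These ages take C1D1 as the start of treatment, and the 28-day cap reads footnote D the same way. If the anchor were instead a first valproic acid dose given at or after enrollment, a 14-day-old test would still fail 4.1.8.

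Three stronger readings are not supported:
- A reader might add the 2 weeks of footnote A to the 4 weeks of footnote D and infer a test 6 weeks old. Section 15.3 puts consent before any study-specific procedure, and footnote D puts consent within 4 weeks of treatment, so a study-specific test cannot be that old.
- A reader might infer that the two rules cannot both be met. They can, whenever the gap from enrollment to treatment is 7 days or less.
- A reader might infer that the registration checklist cannot verify the criterion. Section 5.1 names a completed checklist but does not show its contents.

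The consequence concerns safety and eligibility. The endpoint, sample size, power and type I error are not affected.

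**What to change.** Reconcile 4.1.8 with footnotes A and G so that the same window, anchor and sample type appear in each place. Define the anchor explicitly, stating whether start of treatment means the first valproic acid dose or C1D1. Mark the test in the Table 15 column where it is then due. If that falls after enrollment, the calendar should show it as required before dosing, not only at baseline. The sponsor's clinicians decide which window applies.

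The cost is a wording change in 4.1.8 and the calendar and, for some women, at most one repeat test.

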5 STUDY ENTRY AND WITHDRAWAL PROCEDURES

5.1 Registration Procedures

To register a patient, the study team will provide the following to the registrar at VCU Massey Cancer Center [REDACTED]

- Registration cover sheet
- Completed eligibility checklist
- Signed & dated informed consent form

The registrar will complete the registration process by assigning a study ID number and forwarding the “Confirmation of Registration” form to the registering study team.

No patient may begin study treatment until the Confirmation of Registration assigning a study ID number has been received from the registrar. The registering study team will enter into the OnCore database the patient’s initial enrollment data (demographics, consent, eligibility, on study, treatment assignment) within 24 hours of registration and before treatment begins.

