6.3 Radiographic Evaluations

- 6.3.1 MRI of the brain obtained within 3 weeks prior to entry into the protocol can be used as baseline staging evaluation. In the event that MRI scans cannot be performed, contrast-enhanced CT scans can be used. If scans were obtained from another institution, copies should be obtained and maintained in the research files.
- 6.3.2 A reasonable dose of corticosteroids will be determined on clinical grounds for each patient. An effort will be made to keep the patient on this steroid dose for at least 5 days prior to the next MRI or contrast-enhanced CT scan. If it is not possible to keep the steroid dose constant for 5 days then the MRI scan will be delayed until the dose has been stable for 5 days.

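### The baseline scan window is tied to enrollment, not first dose, so tumor growth before the combination starts can count toward progression in the 6-month PFS endpoint

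*Combined protocol and SAP*

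**What the plan says.** Two places set the baseline scan window, and both anchor it to study entry. Section 12, note I: "MRI or contrast-enhanced CT within 3 weeks prior to enrollment". Section 6.3.1: "MRI of the brain obtained within 3 weeks prior to entry into the protocol can be used as baseline staging evaluation".

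The endpoint clock starts later. Sections 3.2 and 10.4.2 measure PFS from the start of study treatment. Section 6.2 states that "The first cycle begins once therapy begins with all 3 agents", and Section 6.2.1 adds a waiting condition: "Initiation of sorafenib and sildenafil will not take place until valproic acid levels are" at or above the laboratory's lower limit, which it says generally takes 5-7 days. Section 6.2 allows this titration before enrollment but does not require it.

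Enrollment comes before dosing. The registration packet in Section 5.1 includes the "Signed & dated informed consent form", and the same section states: "No patient may begin study treatment until the Confirmation of Registration assigning a study ID number has been received from the registrar". The only limit on the interval from enrollment to first dose is indirect. Note D requires consent "Within 4 weeks prior to initiation of study treatment", and consent cannot come after registration.

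Table 13 defines progression by a rise of at least 25% in the summed products of diameters of enhancing lesions, and it names the baseline scan or best response as the reference. Section 10.4.1 also includes the baseline measurements in the reference for the end of stable disease. Section 10.4 sets re-evaluation every 8 weeks.

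**The concern.** The baseline scan supplies the measurement against which the primary endpoint is judged, yet its permitted age is not tied to the date on which the endpoint clock starts. If the tumor grows between the scan and C1D1, the first on-treatment scan at about week 8 carries that growth as well as any growth on the combination. A patient can then cross the 25% threshold partly because of growth before the three drugs were given together.

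Other baseline items are tied to the start of treatment: C1D1 laboratory tests (note B), the pregnancy test (4.1.8), steroid dose (4.1.3) and consent (note D). The scan is not. The visit near C1D1 in note E checks neurologic stability but does not re-measure the tumor. Section 10.4 lets treatment continue after an equivocal scan, but if the next scan confirms progression it is back-dated to the earlier one, and the baseline is not reset.

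What is at stake is power. The design has little to spare above 80%, and the unselected cohort closes at 3 or fewer successes among 16.

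**Working it through.** **Plan's own design (Section 13.2).** p0 = 0.20, p1 = 0.40, one-sided 5%, power at least 80%; stop at 3 or fewer of 16; success at 11 or more of 33. The exact two-stage probability of success is the sum over x = 4 to 16 of P(X1 = x) × P(X2 ≥ 11 − x), with X1 ~ Bin(16, p) and X2 ~ Bin(17, p). It gives 0.0475 at p = 0.20 and 0.811 at p = 0.40. The stated design reproduces.

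**Scan age at C1D1.**
- Scan to enrollment: at most 3 weeks (note I, Section 6.3.1).
- Enrollment to first dose: at most 4 weeks (note D, with signed consent needed to register).
- Permitted maximum: 21 + 28 = 49 days, or 7 weeks.
- With only titration after enrollment: 21 + 5 to 21 + 7 = 26 to 28 days, or 3.7 to 4.0 weeks.
- If the 3-week window ran to C1D1: 3 weeks.

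**Can growth over such a gap matter against a 25% area threshold?** The documents give no growth rate, so the volume doubling time is an assumption. A 25% rise in area corresponds to a 1.25^1.5 = 1.40-fold rise in volume, and log2(1.40) = 0.483. Growth before C1D1 alone reaches the threshold if the doubling time is no longer than (scan age)/0.483. The last column shows area growth of 2^((2/3) × age/10) − 1 at an assumed 10-week doubling time.

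| Scan age at C1D1 | Doubling time at or below which +25% area is reached | Area growth at 10-week doubling time |
|---|---|---|
| 3 weeks | 6.2 weeks | +15% |
| 4 weeks | 8.3 weeks | +20% |
| 7 weeks | 14.5 weeks | +38% |

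**Illustration of the effect on power.** Assume that each week of extra gap (enrollment to C1D1) removes successes at the PFS hazard implied by the null rate: λ = −ln(0.20)/26 = 0.0619 per week. The observed success rate is then 0.40 × exp(−λg).

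| Average extra gap g | Observed 6-month PFS | Exact power |
|---|---|---|
| 0 | 40.0% | 0.811 |
| 0.5 week | 38.8% | 0.771 |
| 1 week | 37.6% | 0.728 |

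The same shift applied to the null at g = 1 gives 0.20 × exp(−0.0619) = 0.188 and a probability of success of 0.032, against 0.0475. The direction is therefore conservative.

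**The case against.** The strongest reply is that the practical gap is short. Seven weeks needs a scan 21 days before registration, consent and registration on the same day, and first dose 28 days later. Section 15.3 requires consent before any study-specific procedure, so a scan done for the study is capped at 4 weeks by note D; only a routine scan taken before consent can be older. Titration may be finished before enrollment, is not needed for patients already at level (6.2.3), and the calendar lists a valproic acid level at baseline. This stands: 7 weeks is a corner case, and an average extra gap of a week or less is the realistic range.

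The power figures are also high-end. The hazard covers all PFS events, but death before C1D1 cannot enter the trial, and clinical decline is screened by note E and by the Section 4.1.3 requirement of fixed or decreasing steroids "for at least 1 week prior to cycle 1 day 1". Only silent radiographic growth carries over. If the studies behind the 20% null had similar gaps, the comparison is affected less. Both points stand.

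For multifocal disease, Section 10.3 takes the smallest measurement after therapy starts as the reference, so the size mechanism applies mainly to other patients, although new lesions still count.

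A reader might also infer that steroid timing lowers 6-month PFS, because Section 4.1.3 refers to C1D1 while Table 13 refers to the dose at the baseline scan. The documents do not support this. Failing Table 13's wording for stable disease or partial response is not progression, and the endpoint counts only progression or death.

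None of these replies supplies a limit on scan age at C1D1.

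**Conclusion.** The point holds as a cheap improvement to the measurement of the primary endpoint. The plan permits a baseline scan up to 7 weeks old at C1D1, and about 4 weeks old when only titration follows enrollment. Growth before the combination can therefore count toward progression.

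A reader might go further and infer that scans will usually be 7 weeks old, or that pre-dose growth is scored as progression as a rule. The documents support neither. Seven weeks is the permitted extreme, and how often earlier growth tips a patient over 25% cannot be computed from them. Nor is the gap necessarily drug-free, since valproic acid may already be running.

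The bias works against the combination: observed 6-month PFS and power fall, and type I error is not inflated. The illustrated loss, power of 0.77 to 0.73 instead of 0.81, rests on an average extra gap of 0.5 to 1 week and an assumed all-event hazard of 0.062 per week. It is an upper-end figure. The 7-week maximum reads study treatment in note D as C1D1, which Section 6.2 and the calendar support.

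**What to change.** In Section 12, note I, and in Section 6.3.1, require the baseline MRI or contrast-enhanced CT within 3 weeks before cycle 1 day 1. The maximum scan age falls from 7 to 3 weeks. The 16 + 17 patient design, its decision limits and the response criteria stay as they are.

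The cost is a wording amendment, booking scans during or after valproic acid titration, and an occasional repeat scan when first dose is delayed.
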